9.2. RANDOMIZATION

Patient will be randomized in a 1:1 fashion to either repertaxin or placebo. Treatment will be balanced within centers.

A master randomization list will be prepared, randomizing an excess of patients to allow flexible/competitive recruitment within each center. The randomization list will be prepared by **PPD** according to the current version of the Standard Operating procedure (SOP).

The randomization code will be broken at completion of the main part of the study, i.e. when the last patient in has completed his/her 30 days follow-up visit, and once the database has been locked.

9.3. ANALYSIS POPULATION

The Safety population will consist of all patients who received any study medication, and will be based on the treatment actually received. The Safety population will be used to present the demographic and baseline data, and all safety data.

The Intent to Treat (ITT) population will consist of all patients who received any study medication and the transplant, and will be based on the treatment randomized, regardless of the treatment actually received.

The Per-Protocol (PP) population will consist of all patients in the ITT population who did not have any major protocol violations, defined to be:

- Patient who started study drug infusion after reperfusion, i.e. after vascular de-clamping of the first allograft,
- Patients who did not receive the study medication for at least 24 hours,
- Patients without data for PaO₂/FiO₂ ratio at 0 and 24 hours, while on mechanical ventilation,
- Patients who receive Orthoclone OKT3 or Campath induction immunosuppression,

The primary and secondary efficacy analyses will be presented for the ITT population, primarily, and confirmed by the PP population.

9.4. STATISTICAL METHODOLOGY

Appropriate descriptive statistics will be produced, according to the variable. For continuous data the mean, standard deviation, median and range (minimum and maximum) will be presented. For categorical data, frequencies and percentages will be presented. If appropriate, confidence intervals around the mean or the proportions will be presented.

All patient data collected on the CRF will be listed by patient, treatment group and center.

The data for the double-blind phase of the study (up to 30 days post-treatment) will be presented in the clinical study report. Data collected during the open phase of the study (from 1 month up to 12 months) will be presented in an addendum to the clinical study report.

Unless otherwise specified, the significance level used for statistical testing will be 5% and two-sided tests will be used.

9.4.1. Demographic and baseline characteristics

Demographic and baseline characteristics will be summarized for all patients in the Safety population, by treatment group.

9.4.2. Primary efficacy analysis

The PaO₂/FiO₂ ratio will be analyzed separately, at the two time points: 0 hours (ICU admission) and 24 hours after ICU admission. Analysis of variance will be used, including terms for treatment and center. The importance of the treatment by center interaction will be investigated but if this is not significant at the 10% level, this term will be excluded from the final model. If a center by treatment interaction is detected, alternative methods of presentation will be explored. Treatment effect will be primarily compared using a one-sided 0.05 level test and then re-tested for consistency with a two-sided 0.05 level test. Type of transplant (single or bilateral) will then be included in the model of the analysis to explore any possible, even unanticipated, differences due to the specific procedure.

Primarily the data will be analyzed excluding missing data. As confirmatory analysis, the ANOVAs will be performed substituting any missing values by the last observation carried forward (LOCF) method, in patients extubated before 24 hours. If the data are missing due to

patient death, the PaO₂/FiO₂ ratio will be given a zero value. If the data are missing due to lack of recording while on mechanical ventilation, these data will not be substituted.

9.4.3. Secondary efficacy analysis

The PaO₂/FiO₂ ratio will be analyzed, as described for the primary efficacy endpoint, at 48 hours and 72 hours after ICU admission. Analysis of variance will be used, including terms for treatment and center. The importance of the treatment by center interaction will be investigated but if this is not significant at the 10% level, this term will be excluded from the final model. If a center by treatment interaction is detected, alternative methods of presentation will be explored. Type of transplant (single or bilateral) will then be included in the model of the analysis to explore any possible, even unanticipated, differences due to the specific procedure.

Analysis of PGD score will be performed separately at the four time points (0, 24, 48, 72 hours) to test for differences between treatments. Two analyses will be performed at each time-point, using Cochran-Mantel Haenszel statistics, with the first analysis using type of transplant as a stratification factor, and the second using center as a stratification factor.

The time to freedom from mechanical ventilation and the duration of ICU stay will be presented using Kaplan-Meier plots, and will be analyzed using the Median test, to test for differences between treatments. Time to freedom from mechanical ventilation and the duration of ICU stay will also be presented by type of transplant, and the Median test will be performed on each type of transplant, if there are sufficient patient numbers in both categories.

All other secondary endpoints will be presented using appropriate descriptive statistics, and no formal statistical testing will be performed.

ICU mortality and the number of patients who die within the first 30 days post transplant will be tabulated. FEV₁ and FVC at 1 month post-transplant will be presented by type of transplant.

FEV₁ and FVC, BOS score, cumulative acute rejection episodes and patient survival at 6 and 12 months post-transplant will be presented in an addendum to the clinical study report, using descriptive statistics. BOS score, cumulative acute rejection episodes and patient survival will also be presented by type of transplant.

9.4.4. Analysis of the endpoint targeted to the mechanism of action

PMN count in BAL specimen will be presented using descriptive statistics.

9.4.5. Analysis of pharmacokinetic endpoints

Plasma levels of repertaxin (total and unbound) and its major metabolite, DF2243Y, are recorded 24±6 hours and 48 hours from the start of infusion, and then in the interval 2-6 hours after the end of infusion. Data will be summarised using descriptive statistics.

9.4.6. Safety analysis

Safety variables will be presented for the Safety population.

AEs will be presented, by treatment group, in terms of the incidence, severity and relationship to the study drug, overall and by body system and preferred term. SAEs will be presented in the same way.

Laboratory tests are performed at screening and at hospital discharge and shift tables will be used to present shifts from within/outside the normal range between screening and discharge.

Vital signs at each time point, the change in vital signs from screening to each time point, and cardiopulmonary physiologic measurements at each time point will be presented using descriptive statistics.

10. ETHICAL CONSIDERATIONS

10.1. INSTITUTIONAL REVIEW BOARD/RESEARCH ETHICS BOARD

It is the responsibility of the Investigator to obtain approval of the trial protocol/amendments from the Institutional Review Board/Research Ethics Board (IRB/REB).

Prior to the initiation of the study, the Investigator will submit to the appropriate IRB/REB for approval the followings:

- the study protocol,
- the Patient Informed Consent Document and any other written documents to be provided to the patient,
- the current version of the Investigator's Brochure,
- Investigator's current curriculum vitae,
- patient recruitment procedures e.g. advertisements,
- any other requested document(s),

A copy of the IRB/REB approval will be sent to PPD along with all other correspondence with the IRB/REB, including the submission documents. The Investigator should file all correspondence with the IRB/REB in the Investigator Site File. PPD will promptly send to Dompé a copy of the IRB/REB approval.

The study will not be started until full written approval has been obtained from the appropriate IRB/REB. The letter of approval should be dated, and should specify the type (e.g. protocol number) and the date of the documents which were reviewed and approved.

The Investigator will submit any future amendment to the protocol to the IRB/REB which granted the original approval (and other local authorities, according to local regulations). Any amendment will be implemented only when full approval has been obtained from the appropriate IRB/REB, except for those amendments which involve only logistical or administrative aspects of the study.

The Investigator will send to the IRB/REB any updated Investigator's Brochure.

A dated list of the voting members of the IRB/REB who were present when the protocol/amendment was reviewed and approved, including their titles/occupations and institutional affiliations should be provided where possible by the Investigator to PPD prior to study initiation. The Investigator will make all attempts to obtain a statement from the IRB/REB that it is constituted and operates in accordance with the ICH-GCP and any local regulations.

The Investigator will submit required progress reports to the IRB/REB which approved the protocol at least annually, as well as report any serious unexpected ADRs, life-threatening problems or deaths. The Investigator will also inform the IRB/REB of reports of serious unexpected ADRs (provided to him/her by PPD) occurred at other sites participating to this clinical trial and/or in other clinical studies conducted with repertaxin.

The Investigator must inform the IRB/REB of the termination of the study.

10.2. INFORMED CONSENT

No study-related procedures (including non-invasive and diagnostic procedures) will be undertaken prior to completion of the consenting process. Each potentially eligible patient will be informed of the study's objectives and overall requirements. The Investigator will explain the study fully to him/her using the Patient Informed Consent Document. If the patient is willing to participate in the study, (s)he will be requested to give written informed consent after being given sufficient time to consider his/her participation and the opportunity to ask for further details. The Patient Informed Consent Document will be signed and personally dated by **both** the patient and the Investigator.

A copy of the signed form will be provided to the patient and the original signed Patient Informed Consent Document will be retained and filed in the Investigator Site File.

Although nursing staff may be involved in describing the trial to a patient, the Investigator must participate in discussions with the patient **and sign** and personally date the Patient Informed Consent Document.

Individual (i.e. site specific) Patient Informed Consent Forms will be based on a master document provided by PPD and must be approved by PPD prior to submission to the IRB/REB. Any changes requested by the IRB/REB must be approved by PPD prior to the documents being used. A copy of the final, IRB/REB-approved Patient Informed Consent Document must be submitted to PPD prior to initiation of this study.

Where applicable, patients next on the waiting list (max 25 patients) will be pre-consented, i.e. consent is provided before the patient is called into the hospital for transplantation.

10.3. CONFIDENTIALITY

The Investigator must ensure that the subjects' anonymity will be maintained. On the CRFs or other documents submitted to PPD patients should NOT be identified by their names, but by the assigned patient number if randomized plus their initials and date of birth (if not randomized).

If patient names are included on copies of documents submitted to PPD the names (except for initials) will be obliterated or masked and the assigned patient number added to the document.

The Investigator should keep a separate log (Patient Master List) of patient's codes, names, addresses, telephone number and hospital number (if applicable). Documents that are collected but not required for submission to PPD (e.g. signed Patient Informed Consent Forms) should be maintained by the Investigator in strict confidence.

10.4. COMPENSATION FOR MEDICINE-INDUCED INJURY AND INDEMNIFICATION

Before the trial formally starts, Dompé will take out an insurance contract covering the amount requested by the respective national/federal laws for patients participating in clinical trials. The insurance contract will also cover the Investigator/Institution against claims arising from the trial, except for claims that arise from malpractice and/or negligence, including violations of the study protocol.

Should any patients suffer adverse effects as a direct consequence of the Investigational Product administration in accordance with the protocol, Dompé will reimburse for hospital medical costs required for diagnosis and treatment. Medical treatment shall be provided primarily through the study center.

Dompé will not provide for the costs of medical care unrelated to the study.

In case of questions about medical care, cost for medical care or insurance, patients can talk to their Investigator. Contact details will be given in the Patient Informed Consent Document.

11. DATA HANDLING AND RECORD KEEPING

11.1. CASE REPORT FORMS COMPLETION

CRFs will be supplied by PPD . CRFs are the sole property of PPD and should not be made available in any form to third parties, except for authorized representatives of appropriate Health/Regulatory Authorities, without written permission from PPD .

A CRF is required and should be completed for each included patient. The Investigator will be responsible for the accuracy of the data entered in the CRFs. All entries must be written in ***ENGLISH*** in black ink. Source documents should be available to support all the data recorded in the CRF. Location of source data, including those for which the CRF might be accepted as being the sole source document, will be specified and listed at the center Initiation Visit.

The CRF must be available for review/collection to designated PPD representatives at each scheduled monitoring visit.

11.2. DATA MANAGEMENT

Data management of the CRFs will be performed by PPD and will be split into two distinct phases.

For the blinded (main) part of the study the CRF pages for all patients up to the month 1 visit will be data-entered (double data entry) into the study database, and the data will be verified for missing data, inconsistencies, and for any necessary medical clarifications.

Queries arising from these checks will be sent to the Investigator for response and signature. All possible attempts should be made by the Investigator to complete and return the signed responses as instructed to PPD within the requested timeframes.

Once all data queries pertaining to the blinded part of the study have been resolved, the study will be declared to be "clean", and the study data will be locked ready for analysis. Following the data lock the study blind will be broken and each patient's medicinal assignment (i.e. repertaxin or placebo) will be revealed to the appropriate Investigator.

The CRF pages for both follow up visits i.e. months 6 and 12 will be entered into a different location of the same database using the same procedure as described above. Furthermore when the last patient's month 12 visit has been "cleaned" the database will be locked ready for the final analysis.

After the database lock has been achieved, the Investigator may archive the copies of the CRFs retained at the center. The original CRFs collected by PPD will be archived by Dompé.

All data management will be conducted in accordance with good clinical, scientific and data management principles and in compliance with current PPD SOP.

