3. OVERALL STUDY DESIGN AND PLAN DESCRIPTION

3.1. STUDY DESIGN

The study will be a phase 2, multi-center, randomized, double-blind, placebo-controlled, parallel-group (two arms) study.

It will involve 100 lung transplant recipients, randomly assigned in a 1:1 ratio to receive repertaxin or placebo, by continuous i.v. infusion for a period of 48 hours starting approximately 2 hours before reperfusion of the (first) transplanted lung occurs. The experimental treatment will be additional to the standard treatment of lung transplant recipients.

Recruitment will be competitive among the study sites, until the planned number of patients is enrolled. Competitive recruitment has been chosen to increase the speed of recruitment and to account for any difference in transplant rate among study sites.

Each patient will be involved in the study for 48 hour treatment, for measurements up to hospital discharge, and then for three visits (@ 1, 6, and 12 months post-transplant).

The double-blind will be maintained for the main part of the study only, i.e. up to the 1 month (at least 30 days post-transplant) follow-up visit of the last patient in. After database lock the randomization code will be broken and the results of the blind phase will be analyzed and the study will proceed in an open fashion.

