3.2. STUDY TIME TABLE

- Actual starting date (first-patient-in): 1 May 2005
- Projected completion of patient accrual (last-patient-in): September 2006
- Projected study end date (last-patient-last-visit): September 2007

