7.9. MONTHS 6 AND 12 POST-TRANSPLANT

Patient will attend the center at months 6 and 12 +/- 2 weeks post-transplant. The following measurements will be performed as per center practice (unless otherwise specified) and recorded in the CRF:

- FEV₁, FVC, BOS score will be assessed at each visit. BOS score will be evaluated according to Estenne et al. (2002).
- Acute, biopsy proven rejection episodes diagnosed according to Yousem et al. (1996). Cumulative assessment at each visit.

For all measurements above, actual date of assessment will be recorded in the CRF. Diagnosis and treatment of acute rejection, if any, will be also recorded in the CRF.

Patient vital status, as well as any AEs occurring during the intervals between study visits that the Investigator assesses as at least possibly related to the Investigational Product will be recorded at each visit.

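### Site investigators are given each patient's assignment after the Month 1 lock, with no stated reason, while exploratory Month 6 and 12 assessments are still being collected

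*Protocol*

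**What the plan says.** Protocol 3.1 keeps the blind "up to the 1 month (at least 30 days post-transplant) follow-up visit of the last patient in". Once that part of the database is locked, the code is opened for the main-phase analysis, after which "the study will proceed in an open fashion". Protocol 6.1.6 and 9.2 place the code break at the same point, the synopsis and 9.4 call what follows an open phase, and SAP 3.1 agrees. Protocol 11.2 adds who is told: each patient's assignment "will be revealed to the appropriate Investigator".

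Month 6 and 12 visits continue after that, with their own data entry and second lock (Protocol 11.2). Under Protocol 7.9, "BOS score will be assessed at each visit", along with FEV1, FVC and a cumulative count of biopsy-proven rejection. Measurements follow center practice unless the protocol specifies otherwise. The same section, with 8.3.1, limits late AE recording to events the investigator considers at least possibly related. SAP section 5 leaves the choice of the FEV1 baseline for BOS to center practice.

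Protocol 4.2.1.2 labels these endpoints exploratory. Protocol 9.4.3 reports the Month 6 and 12 results descriptively, in an addendum.

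**The concern.** Breaking the code for the Month 1 analysis and telling sites are separate steps, and only the first is needed for the report. The documents give no reason for the second. Treatment is a single 48-hour infusion, nothing in the later schedule depends on the arm, and Protocol 8.2 already provides sealed envelopes for emergencies.

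Three late items involve center judgement:

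- the decision to biopsy, since no surveillance schedule is given and rejection counts only if biopsy proven;
- the FEV1 value used as the BOS baseline;
- AE causality, which after the early period decides whether an event is recorded at all.

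No blinded assessor is named for any of these; the only one in the protocol is the radiologist who validates the early chest X-rays (Appendix 1). Because the code is broken on one calendar date, early enrollees reach Month 12 under the blind and late enrollees do not. The addendum would then contain both kinds of assessment.

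**Working it through.** **Inputs from Protocol 3.2.** "Actual starting date (first-patient-in): 1 May 2005"; "Projected completion of patient accrual (last-patient-in): September 2006"; "Projected study end date (last-patient-last-visit): September 2007". The accrual length D therefore runs from 488 days (last patient on 1 September 2006) to 517 days (30 September 2006). The Month 1 visit falls at v = 30 to 35 days (Appendix 6).

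**Check of the plan's timetable.** 1 to 30 September 2006 plus 365 days is 1 to 30 September 2007, which matches the projected end date.

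**Assumptions, not in the documents.** Accrual is uniform as a base case. The lag from the last Month 1 visit to lock and code break is 1 to 4 months (30.44 days per month), with 0 and 6 months shown for reference. All patients are taken to reach their visits.

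**Share of visits that are open.** The code breaks on day L = D + v + lag. A visit m days after transplant is open if entry + m > L, so under uniform accrual the share is (m − v − lag)/D, floored at 0. I use m = 365.25 for Month 12 and 182.6 for Month 6.

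- Highest Month 12 share at a 1-month lag: (365.25 − 30 − 30.44)/488 = 62.5%.
- Lowest Month 12 share at a 4-month lag: (365.25 − 35 − 121.75)/517 = 40.3%.

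| Lag to lock | Month 12 visits open | Month 6 visits open |
|---|---|---|
| 0 months | 63.9–68.7% | 28.5–31.3% |
| 1 month | 58.0–62.5% | 22.7–25.0% |
| 2 months | 52.1–56.2% | 16.8–18.8% |
| 3 months | 46.2–50.0% | 10.9–12.6% |
| 4 months | 40.3–43.8% | 5.0–6.3% |
| 6 months | 28.6–31.3% | 0% |

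**Sensitivity to accrual shape (D = 517, v = 30).** Let c = (L − 365.25)/D. At a 1-month lag c = 0.410; at 4 months c = 0.587.

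- Linearly rising accrual, share 1 − c²: 83% and 66%.
- Linearly falling accrual, share (1 − c)²: 35% and 17%.

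**Two illustrative lock dates (D = 517, uniform accrual).**

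- Lock on 30 November 2006: Month 12 visits 304/517 = 59% open; Month 6 visits 121/517 = 23%.
- Lock on 31 January 2007: Month 12 visits 242/517 = 47% open; Month 6 visits 59/517 = 11%.

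**Follow-up time, the better unit for rejection.** Rejection is counted cumulatively, so what matters is how much of the first year falls after the code break. Affected patients have on average half the maximum open time before Month 12.

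- 30 November lock: (304 × 152)/(517 × 365) = 24%.
- 31 January lock: (242 × 121)/(517 × 365) = 16%.

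**The case against.** The open phase is a declared design choice, stated consistently in both documents, and a sponsor may reasonably accept open follow-up in a phase 2 trial of a short infusion. The primary endpoint, PGD score, ventilation time, ICU stay and 30-day mortality are all locked before the code break. The late endpoints are exploratory and descriptive. BOS follows published criteria based on FEV1 thresholds, rejection needs biopsy proof under a published grading scheme, and survival is objective. All of this stands, and it keeps the point minor. It does not supply a reason for telling sites, and it leaves the three center judgements exposed.

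A reader might infer that about half of all late BOS and rejection assessments are open-label. The documents do not support that. A figure near half fits Month 12 visits under one set of assumptions; Month 6 visits are much less affected, and rejection episodes diagnosed before the code break were assessed blind.

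A reader might also infer that mixing blinded and open visits biases the comparison in itself. It does not: whether a visit is open depends on enrollment date, and treatment is balanced within centers (Protocol 9.2). Bias requires assessors to act differently once they know the arm. Nor can it be said that the mixture will go unflagged, because the Month 12 analyses belong to a separate SAP (SAP 1.1) that is not available here.

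**Conclusion.** The point holds as a low-cost improvement, not as an error or a contradiction. Sites are unblinded earlier than the Month 1 analysis requires, without a stated reason, and this leaves avoidable room for assessor bias in a few center-judged items.

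The size rests on assumptions the documents do not settle. The estimate of about 40 to 63% of Month 12 visits assumes the projected dates, uniform accrual and a 1 to 4 month lock lag; accrual shape alone widens it to 17 to 83%. The Month 6 share of 11 to 23% and the 16 to 24% of first-year follow-up time apply to the two illustrative lock dates. These figures measure exposure to open assessment. They do not estimate a bias, and the documents give no basis for one. A reader who concludes that the trial's main efficacy result is compromised would be wrong.

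**What to change.** Amend the Protocol synopsis, 3.1, 6.1.6, 9.2, 9.4 and 11.2, together with SAP 3.1, so that after the Month 1 lock only the sponsor and CRO analysis team is unblinded. Investigators and site staff would not receive patient-level assignments until the Month 12 lock. Keep the emergency envelopes in Protocol 8.2 as they are. All seven places need the change, because each describes the code break or the open phase and a partial edit would create contradictions. The share of late visits assessed by sites holding the assignments would then be zero, apart from any emergency unblinding.

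The cost is a short amendment, with no extra staff or procedures. SAP 1.1 puts recruitment at about 60 patients when it was written, before the Month 1 lock, so there was time to make it. There are two downsides. Sites learn assignments later: from a lock at the end of November 2006 to the last projected visit at the end of September 2007 is about 10 months, plus whatever time Month 12 cleaning takes. Month 1 results must also be shared with sites without patient-level codes.
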